2.5.2 Statistical hypothesis, model, and method of analysis

The primary analysis will describe the test for null hypothesis (H0):ARR >=0.18 versus alternative hypothesis (H1): ARR<0.18.

[figure not shown]
In the analysis, the response variable is the number of confirmed relapses observed from each participant and the participant's time in study (natural log of time in years) is used as an offset variable to adjust for the varying lengths of participant's time in the study. The adjusted ARR (i.e., model-based estimate adjusted for covariates) along with the corresponding one-sided 95% confidence interval and one-sided p-value for hypothesis testing will be obtained.

A negative binomial model with log-link and subject's time in study (as natural log of time in years) will be used as an offset with number of relapses in previous year, baseline EDSS, baseline number of T1 Gd-enhancing lesions, the participant's age at baseline and prior MS therapies (fumarates or fingolimod) as covariates.

In addition, ARR time-based and subject-based will also be summarized based on only confirmed relapses. Below are the definitions time-based and subject-based ARR:

- ARR (time-based) is calculated by taking the total number of relapses observed for all subjects, divided by the total number of days in study of all subjects and multiplied by 365.25 days.
- ARR (subject-based) is the individual subject ARR which is calculated by taking the total number of relapses observed for a subject divided by the total number of days in study of that subject and multiplied by 365.25.

2.5.3	CCI		
2.5.4	CCI		
missing a	t random, and constant relapse rate over time.	drop-out,	information is
2.5.5	CCI		

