12.4 Analysis of the primary endpoint(s)

The primary objective of the study is to determine the effectiveness of ofatumumab 20 mg s.c. administered every 4 weeks in subjects with relapsing forms of MS who have breakthrough treatment response on fumarate-based RMS approved therapies or fingolimod as evaluated by the annualized relapse rate (ARR, based on confirmed relapses) in patients with relapsing MS. The primary analysis will describe the ARR with one-sided 95% confidence bound and test for null hypothesis (H₀): ARR \geq 0.18 versus alternative hypothesis (H₁): ARR \leq 0.18.

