12.4.2 Statistical model, hypothesis, and method of analysis

The primary analysis will describe the test for null hypothesis (H0): ARR >=0.18 versus

alternative hypothesis (H1): ARR<0.18. The ARR will be estimated for the entire duration by a negative binomial model with log-link and subject's time in study (as natural log of time in years) will be used as an offset with number of relapses in previous year, baseline EDSS, baseline number of T1 Gd enhancing lesions and the patient's age at baseline, prior MS therapies (fumarates or fingolimod) as covariates. The list of covariates in the model can be modified based on convergence of the statistical model. In addition, ARR will be calculated as number of confirmed relapses divided by time in study in year will also be presented for the entire duration. The ARR will also be summarized by yearly interval starting from the first dose of ofatumumab.

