2.5.1 Primary endpoint

The primary endpoint of the study is the annualized relapse rate (ARR, based on confirmed relapses), which is defined as the number of confirmed MS relapses in a year. In the primary analysis, the ARR is estimated based on the FAS using individual relapse count as the response variable with natural log of time in study in years as an offset variable.

Two variables are required for the calculation of the estimated average ARR (excluding covariates):

- The cumulative number of confirmed MS relapses by subject based on EDSS will be derived. All confirmed relapses with a start date on or after the date of first administration of study drug and prior to the efficacy cutoff date will be included in the analysis. Additional details are provided in Section 5.1.4 and Section 5.4.1.
 - The definition of a confirmed MS relapse is one accompanied by a clinically relevant change in the EDSS assessment, i.e. an increase of at least 0.5 points on the EDSS (total) score, or an increase of at least 1 point on at least two Functional scores (FSs), or an increase of at least 2 points on at least one FS, excluding changes involving bowel/bladder or cerebral FS, compared to the last EDSS assessment taken in the absence of (confirmed or unconfirmed) relapse and prior to the current relapse. EDSS obtained on the date as indicated on the Summary of MS Relapse eCRF page will be used. If such EDSS assessment is missing or not meeting the criteria to confirm the relapse, all other EDSS assessments taken within 30 days from the relapse start date (i.e., EDSS assessment date relapse start date <=30) and before the relapse end date (EDSS assessment date < relapse end date) will be checked. If at least one of such available EDSS assessments meets the criteria, the relapse is a confirmed relapse. Otherwise, the relapse is considered an unconfirmed relapse.

• The time-in-study by subject will be used as an offset variable to adjust for the various length subjects have been observed and at-risk of a confirmed MS relapse in the study. Time in study for ARR will be calculated as (end of efficacy cutoff date – first dose date+1)/365.25. Definition of efficacy cutoff date is provided in Section 2.1.

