5.4 Statistical models

5.4.1 Primary analysis

[figure not shown]
The primary analysis will describe the test for null hypothesis (H0):ARR >=0.18 versus alternative hypothesis (H1): ARR<0.18. The ofatumumab treatment effect will be estimated for the entire duration by a negative binomial model with log-link and subject's time in study (as natural log of time in years) will be used as an offset with number of relapses in previous year, baseline EDSS, baseline number of T1 Gd-enhancing lesions, the participant's age at baseline and prior MS therapies as covariates.

CCI		
5.4.2	Supplementary analysis for primary endpoint	
CCI		
		·

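### Is the one-sided 5% error lost because the visible plan does not say at which covariate values the adjusted ARR tested against 0.18 is evaluated?

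*SAP*

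**What the plan says.** The hypothesis in SAP 2.5.2 is "The primary analysis will describe the test for null hypothesis (H0):ARR >=0.18 versus alternative hypothesis (H1): ARR<0.18". Protocol 12.4 sets the level: "The primary analysis will describe the ARR with one-sided 95% confidence bound". The trial has one arm, so 0.18 is a fixed external number.

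The test uses "The adjusted ARR (i.e., model-based estimate adjusted for covariates) along with the corresponding one-sided 95% confidence interval and one-sided p-value for hypothesis testing". The model has a log link, an offset of log years in study, and five covariates: relapses in the previous year, baseline EDSS, baseline T1 Gd lesions, age, and prior therapy (fumarates or fingolimod). SAP 5.4.1 repeats that the effect "will be estimated for the entire duration by a negative binomial model with log-link".

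The unadjusted rates carry no test. SAP 2.5.2 adds: "In addition, ARR time-based and subject-based will also be summarized based on only confirmed relapses". Protocol 12.4.2 likewise says that "ARR will be calculated as number of confirmed relapses divided by time in study in year will also be presented for the entire duration".

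The nearest thing to a statement of the target is in SAP 2.5.1, on the FAS: "Two variables are required for the calculation of the estimated average ARR (excluding covariates". That section sends the reader to SAP 5.1.4 and 5.4.1 for further detail. The visible part of 5.4.1 is one paragraph followed by blacked-out text. A figure is also missing from 2.5.2, between the hypothesis and the model description.

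**The concern.** In a two-arm trial the covariate values at which a log-link model is evaluated drop out of the rate ratio. Here they do not, because the adjusted rate is compared directly with 0.18. Three readings of an adjusted ARR are possible.

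1. **At mean covariates.** The exponential is convex, so this rate lies below the FAS-average rate whenever the covariates are prognostic. The bias favours rejecting H0.
2. **As a least-squares mean with prior therapy weighted 50/50.** The result can lie above or below the FAS average, depending on the actual therapy split and effect.
3. **As the average of model-predicted rates over the FAS.** This targets the FAS average itself.

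This is the only confirmatory test, and the planning gap is narrow. The assumed ARR is 0.16 (Protocol 12.8), so the log distance to the threshold is ln(0.18/0.16) = 0.118. A small shift in the tested quantity matters on that scale.

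**Working it through.** **Inputs from the documents.** About 555 subjects (Protocol 3, SAP 1.1); 96 weeks, so T = 672/365.25 = 1.84 years; threshold 0.18; one-sided 5%. The sample-size basis is blacked out, so the plan offers no figure to reproduce on this point.

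**Assumptions.** Dispersion k, the SD s of the log-rate explained by the covariates, and the therapy split and effect. None is in the documents.

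**Reading 1, analytic.** Let the true FAS-average ARR be exactly 0.18 and the linear predictor be normal with SD s.

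- Rate at mean covariates = 0.18 × exp(−s²/2).
- SE of the log-rate = √(1/(555 × 1.84 × 0.18) + k/555). With k = 0.5 this is √(0.00544 + 0.00090) = 0.080.
- Error = Φ(−1.645 + (s²/2)/SE).

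| s | rate at mean covariates | error, k = 0.5 | error, k = 1 |
|---|---|---|---|
| 0.1 | 0.179 | 5.7% | 5.6% |
| 0.2 | 0.176 | 8.2% | 7.9% |
| 0.3 | 0.172 | 14.0% | 13.2% |

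At s = 0.3 the shift of 0.045 is 38% of the 0.118 planning distance (0.045/0.118).

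**Reading 1, simulated.** This used 555 subjects, 10% dropout, the five slopes estimated by maximum likelihood, and 2,000 trials per cell (Monte Carlo SE about 0.5 points at 5%). With k = 0.5 the error was 8.4% with no covariate effect, 10.4% at s = 0.15, 19.0% at s = 0.30 and 42.3% at s = 0.45. The 8.4% arises from estimating the slopes, not from prognostic covariates.

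**Reading 2.** The therapy effect alone shows the direction. Let a share p be on fingolimod with rate ratio R. The fumarate rate is 0.18/(1 − p + pR), and the 50/50 value on the log scale is that rate times √R.

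- p = 0.20, R = 1.5: 0.18/1.10 × 1.225 = 0.200, above 0.18.
- p = 0.35, R = 1.3: 0.18/1.105 × 1.140 = 0.186.
- p = 0.70, R = 1.3: 0.18/1.21 × 1.140 = 0.170, below 0.18.

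With the other covariates added as weak predictors, the simulated mean estimates were 0.194, 0.180 and 0.165. The errors at k = 0.5 were 0.9%, 5.3% and 23.2%. This reading can therefore be conservative, near nominal or inflated.

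**Reading 3, simulated.** Mean estimates were 0.179 to 0.180. Error was 4.6% to 6.4% when the variance counts covariate sampling, and 4.9% to 6.8% when covariates are treated as fixed.

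**Is the rule absent or hidden?** Three features of the SAP show that primary-model and model-code text has been withheld. Section 5.4.1 breaks off into a redaction. The document history for amendment 3 says Section 2.5 now gives an order for dropping covariates on non-convergence, and no such order is in the visible part of 2.5. Sections 5.4.3 and 5.4.4 are headed as sample SAS code and show none. How an adjusted rate is evaluated is the kind of detail that such code carries.

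**The case for a change.** The strongest case for a change is that the only confirmatory p-value depends on a choice the reader cannot see, that the most familiar error runs in the sponsor's favour, and that one sentence would settle it. Protocol 12.4.2 also lets the covariate list change if the model does not converge. At mean covariates, dropping a prognostic covariate would change the quantity tested, whereas averaged over the FAS the target stays the same.

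The conditional arithmetic stands: two separate calculations agree on the analytic figures for reading 1 and, at s = 0.3, on a simulated 19%. What does not stand is the step from not visible to wrong. Text blacked out for publication is not missing from the plan, and no visible rule directs the analyst to a biased evaluation. Nor is it true that the 5% level fails whenever the rate is not averaged over the FAS, since the 50/50 least-squares mean gave 0.9% and 5.3% in two scenarios.

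The bias argument also needs H0 to concern the FAS average. The only visible support for that is the phrase in SAP 2.5.1, which is not a formal estimand. If it does fix the target as an average, it points to reading 3, where the error is near nominal. If it does not, the claim that readings 1 and 2 miss the target is weaker.

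**Conclusion.** The concern is sound as a conditional statement but is not shown to be a defect, and no change to the plan follows. If the adjusted ARR were read at mean covariates, the one-sided error for the FAS-average ARR would exceed 5%. Analytically the excess is 0.7 points at s = 0.1 and 9 points at s = 0.3, and it is larger once slope estimation is included. If it is averaged over the FAS, the error is about 5% to 7%. These sizes rest on an assumed dispersion, covariate SD and therapy split.

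The rule that decides between the readings belongs in the part of SAP 5.4.1 that is not public, and the visible wording is compatible with the averaged reading. The plan also has a check of its own: the time-based crude ARR, total confirmed relapses over total time, is prespecified beside the adjusted value. It carries no test, but a gap such as 0.172 against 0.180 would show in the report. What remains is a question of detail for whoever holds the unredacted SAP.

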2.6 Analysis of the key secondary objective

There is no key secondary objective defined for this study.

2.7 Analysis of secondary efficacy objective(s)

No other secondary efficacy objectives were analyzed.

2.8 Analysis of secondary objective(s)

The secondary objective is to evaluate the safety of ofatumumab 20 mg s.c. administrated every 4 weeks in subjects with relapsing forms of MS who had breakthrough disease on fumarates or fingolimod.

Below are the secondary endpoints defined to evaluate secondary objective.

- Proportion of subjects with adverse events, including injection related reactions
- Proportion of subjects with laboratory or vital signs results meeting abnormal criteria
- The proportion of subjects discontinuing treatment due to insufficient effectiveness (lack of efficacy) or tolerability/safety reasons

Since these objectives are related to safety, details on analysis is provided in safety Section 2.9.

2.9 Safety analyses

Safety analyses will be conducted using the safety (SAF) set. Unless explicity stated otherwise, all safety analyses will be performed using all data collected in the database up to

The assessment of safety will be primarily based on the frequency of adverse events (including death and non-fatal serious adverse events). Additional safety assessments include laboratory tests, physical examination (including examination of skin), vital sign measures, ECG evaluations and assessment of suicidality. Clinically significant findings in these additional safety assessments will be reported as adverse events and analyzed as such. In addition all safety assessments will be summarized or listed as appropriate.

2.9.1 Adverse events (AEs)

An adverse event (AE) is any untoward medical occurrence (i.e., any unfavorable and unintended sign [including abnormal laboratory findings], symptom or disease) in a subject or clinical investigation of a subject after providing written informed consent for participation in the study. That means that a subject can report AEs before having started study medication. For reporting purposes, the main focus will be on treatment emergent adverse event (TEAE), defined as any adverse event which started on or after the day of first dose of study medication.

TEAEs and serious TEAEs up to and including safety cut-off date will be included in the analyses (see detailed explanation in Section 2.9 for safety cut off date).

AEs will be reported by primary system organ class (SOC) and preferred term according to the Medical Dictionary for Regulatory Activities (MedDRA). The MedDRA version is 27.0.

The number and percentage of subjects reporting any TEAEs (referred to as incidence of any TEAEs later) will be summarized by primary SOC and preferred term.

Separate summaries will be provided for:

- overview of TEAEs,TEAEs by primary SOC,most common TEAEs by preferred term (≥ 2%), most common TEAEs by preferred term (≥ 2%) and last prior DMT, TEAE by last prior DMT, TEAE by duration of washout
- serious TEAEs by primary SOC and preferred term, serious TEAEs by last prior DMT, serious TEAEs by duration of washout, deaths by primary SOC and preferred term,
- drug related TEAEs by primary SOC and preferred term,
- TEAEs leading to treatment interruption and permanent discontinuation of study drug by primary SOC and preferred term, TEAEs leading to treatment interruption and permanent discontinuation of study drug by last prior DMT, TEAEs leading to treatment interruption and permanent discontinuation of study drug by duration of washout, any TEAEs will also be summarized by primary SOC, preferred term, and maximum Common Terminology Criteria for Adverse Events (CTCAE) grade. Missing CTCAE grade will not be imputed.

If a subject reported more than one adverse event within the same primary system organ class, the subject will be counted only once with the maximum CTCAE grade at the system organ class level, where applicable.

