3 = severe: prevents normal activities

4 = life-threatening

- Its relationship to the study treatment.
- Its duration (start and end dates) or if the event is ongoing, an outcome of not recovered/not resolved must be reported
- Whether it constitutes a SAE (see Section 10.1.2 for definition of SAE) and which seriousness criteria have been met
- Action taken regarding with study treatment

All adverse events must be treated appropriately. Treatment may include one or more of the following:

- No action taken (e.g. further observation only)
- Drug interrupted/withdrawn
- Concomitant medication or non-drug therapy given
- Subject hospitalization/subject's hospitalization prolonged (see Section 10.1.2 for definition of SAE)
- Its outcome (not recovered/not resolved; recovered/resolved; recovered/resolved with sequelae; fatal; or unknown).

Conditions that were already present at the time of informed consent should be recorded in medical history of the subject.

Adverse events (including lab abnormalities that constitute AEs) should be described using a diagnosis whenever possible, rather than individual underlying signs and symptoms.

Adverse event monitoring should be continued for at least 100 days following the last dose of study treatment.

Once an adverse event is detected, it must be followed until its resolution or until it is judged to be permanent (e.g. continuing at the end of the study), and assessment must be made at each visit (or more frequently, if necessary) of any changes in severity, the suspected relationship to the interventions required to treat it, and the outcome.

Information about adverse drug reactions for the investigational drug (ofatumumab) can be found in the Investigator's Brochure (IB). This information will be included in the subject informed consent and should be discussed with the subject during the study as needed. Any new information regarding the safety profile of ofatumumab that is identified between IB updates will be communicated as appropriate, for example, via an Investigator Notification or an Aggregate Safety Finding. New information might require an update to the informed consent and has then to be discussed with the subject.

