12.5.2 Safety endpoints

For all safety analyses, the safety set will be used. All listings and tables will be presented for all subjects in the safety set. Unless explicitly otherwise stated, only data up to and including the safety cutoff of 100 days after permanent study drug discontinuation will be included in the analysis and data beyond this time point for a patient will be excluded from safety analysis. In addition, a separate summary for death including on treatment and post treatment deaths will be provided. In particular, summary tables for adverse events (AEs) will summarize only ontreatment events, which started or worsened during the on-treatment period (treatment-emergent AEs).

The on-treatment period for safety analysis lasts from the date of first administration of study drug to 100 days after the date of the last actual administration of study drug.

The sensitivity analysis for safety endpoints based on modalities for data collection (on-site or remotely) and based on pandemic phase indicator may be performed if there is sufficient data.

Adverse events

All information obtained on adverse events will be displayed. The number (and proportion) of subjects with AEs of special interest/related to identified and potential risks will be summarized.

A subject with multiple AEs within a primary system organ class is only counted once towards the total of the primary system organ class. Summary tables for AEs will include only AEs that started or worsened during the on-treatment period, the *treatment-emergent* AEs.

The incidence of treatment-emergent AEs (new or worsening from baseline) will be summarized by system organ class and/or preferred term, severity (based on CTCAE grades), type of AE, relation to study drug.

Adverse events, Serious AEs and adverse events of special interest (AESI) during the ontreatment period will be tabulated.

All deaths (on-treatment and post-treatment) will be summarized. All AEs, death and serious AEs (including those from the pre and post-treatment periods) will be listed and those collected during the pre-treatment and post-treatment period will be flagged.

Vital signs

Vital signs data may be listed by subject, and visit/time and if ranges are available, abnormalities will be flagged. Summary statistics will be provided by visit/time.

Clinical laboratory evaluations

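### SAP 2.9.1 defines a treatment-emergent AE by start date alone, while protocol 12.5.2 also counts AEs that worsened on treatment, and no visible SAP text declares or explains the change

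*SAP*

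**What the plan says.** Protocol 12.5.2 includes worsening in three places. It restricts AE summary tables to on-treatment events, "which started or worsened during the on-treatment period". Under its adverse events heading it repeats the rule: "Summary tables for AEs will include only AEs that started or worsened during the on-treatment period". It then describes the main tabulation: "The incidence of treatment-emergent AEs (new or worsening from baseline) will be summarized by system organ class". The protocol's on-treatment period runs from first dose to 100 days after the last dose.

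SAP 2.9.1 notes that AEs can be reported before study drug is started. It then narrows the focus to TEAEs, with a TEAE "defined as any adverse event which started on or after the day of first dose of study medication". Worsening is not mentioned. The AE tables are built on that flag: "The number and percentage of subjects reporting any TEAEs (referred to as incidence of any TEAEs later) will be summarized". The same flag carries into the serious, drug-related, interruption or discontinuation, maximum-grade, prior-DMT and washout summaries, and through SAP 2.9.1.1 into the tables for events of special interest.

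SAP 2.8 lists the secondary endpoint "Proportion of subjects with adverse events, including injection related reactions" and refers its analysis to section 2.9. The SAP introduction says that the analysis follows section 12 of the protocol.

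**The concern.** The two documents define the same term differently, and the SAP definition is the one that will be programmed. On this criterion, SAP-defined TEAEs are a subset of protocol-defined ones, so a SAP count can equal the protocol count or fall below it, but cannot exceed it.

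The pre-dose window matters in this design. AEs are collected from consent, screening lasts up to 60 days, and it contains the transition off a fumarate or fingolimod. Protocol 6.6.1 requires AEs during that transition to go on the AE form. An event that begins then and gets worse after ofatumumab is started is one that a worsening criterion exists to catch.

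AE frequency is the main basis of the safety assessment (SAP 2.9) and supplies a secondary endpoint. With a single arm there is no control group in which the same omission would occur.

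**Working it through.** The documents give no figure to reproduce, because the point is about a definition. The check is to take each kind of AE and ask whether each document counts it.

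| AE | Protocol 12.5.2 | SAP 2.9.1 |
|---|---|---|
| Starts on or after first dose | counted | counted |
| Starts between consent and first dose, does not worsen | not counted | not counted |
| Starts between consent and first dose, worsens on treatment, new record opened at worsening | counted | counted |
| Starts between consent and first dose, worsens on treatment, original record kept | counted | **not counted** |
| Condition already present at consent | medical history (10.1.1) | medical history |

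The definitions part company only in the fourth row, so the result depends on how a worsening is recorded.

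**What the documents say about recording.** Protocol 10.1.1 has an AE followed until it resolves or is judged permanent, and says that "assessment must be made at each visit (or more frequently, if necessary) of any changes in severity". Protocol 10.1.3 has progression of an SAE reported as follow-up to the original event. Both suggest one continuing record. The first does not say how a grade change is entered, and the second governs safety reporting rather than start dates on the AE form. No visible text tells sites to open a new AE record when the grade rises.

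**Is worsening restored elsewhere in the SAP?** Not for AEs in the visible text. SAP 2.9.3 does count new or worsening laboratory abnormalities by CTC grade, so the criterion is missing for AEs only.

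**Is the change declared?** The SAP document history for amendments 1 to 4 mentions no change to the TEAE definition. The list under SAP section 4 is not visible, so a declaration there cannot be ruled out.

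**Size.** The input is N of about 555 (protocol section 5).

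- One subject is 1 / 555 = 0.18 percentage points.
- Let s be the share of subjects with at least one worsened pre-dose AE on its original record, and q the share of those with no other TEAE. Subjects losing at least one entry in a preferred-term, grade or seriousness row number 555 × s. The fall in the any-AE proportion is s × q.
- The documents give neither s nor q. Purely as an assumption, s = 1% gives 555 × 0.01 = 5.55, about 6 subjects, and s = 3% gives 555 × 0.03 = 16.65, about 17. They would be spread over different preferred terms, not gathered in one.
- The any-AE proportion would fall by between 0 (q = 0) and s itself (q = 1), that is 0 to 1 point or 0 to 3 points under those two assumptions.

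**The case against.** The strongest reply is that the loss is not shown to occur. Several passages treat worsening as reportable in its own right. The SAE definition in protocol 10.1.2 covers worsening of something pre-existing. Protocol 8.4 has new or worsening findings from additional safety assessments recorded as AEs where they meet the definition. Protocol 9.2.1 has forms updated at the end of safety follow-up for new or worsening events. If sites open a new record at worsening, the SAP's start-date rule already captures the event. This objection stands as a condition on the consequence. It does not remove the difference in wording, and the SAP nowhere says that it relies on such a recording rule.

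Second, the reach is narrow. Only AEs that arise between consent and first dose qualify. Injection-related reactions, which the endpoint names, follow an injection and are unaffected. A subject with any other TEAE over 96 weeks and follow-up still counts in the overall proportion. All of this stands.

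Third, the events are not hidden. Protocol 12.5.2 lists all AEs, with pre-treatment ones flagged. SAP 2.9.1.1.2 summarises all SAEs whatever the safety cut-off. SAP 2.9.2 includes all recorded deaths, and SAP 2.9.4.3 takes discontinuation reasons from the disposition page. This stands too, but listings do not correct the percentages in the TEAE tables.

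A reader might go further and infer that worsened pre-dose events certainly drop out of the secondary endpoint, or that it is biased in the drug's favour by a material amount. The documents support neither. They do not settle the recording rule, they give no rate, and the effect on the any-AE proportion may be nil.

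**Conclusion.** The contradiction is real and should be corrected. The protocol counts AEs that worsened on treatment; the SAP as visible does not, while saying that it follows the protocol's analysis section. If a worsened AE keeps its pre-dose record, it is omitted from the affected preferred-term, maximum-grade, seriousness, relatedness and special-interest rows. The overall proportion with any AE falls only for subjects with no other TEAE.

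The direction is fixed: counts can only be equal or lower. The size is unknown, and the 1% and 3% above are assumptions, not estimates. The conclusion about lost events rests on the recording rule, and the statement that the change is undeclared is limited to the visible text. It would be too strong to infer that the SAP narrows the definition on purpose or conceals events, given the listings, the SAE summary and the unseen list in section 4.

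**What to change.** In SAP 2.9.1, define a TEAE as an AE that either started on or after first dose, or was present before first dose and increased in CTCAE grade on or after it, in both cases up to the safety cut-off. This matches protocol 12.5.2. Apply it to every table that uses the TEAE flag, including the serious, drug-related, maximum-grade, subgroup and special-interest tables.

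State in the same place how worsening is identified in the data, by a new AE record at the grade increase or by a dated grade change on the existing record. This is needed because protocol 10.1.1 lists a grade and start and end dates for each AE but shows no dated grade history. If sites already open a new record, one sentence saying so shows that the start-date rule captures these events. If the narrower definition is intended, SAP section 4 should declare and justify it as a change to the protocol.

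The cost is a short SAP edit and a small programming change, provided that worsening can be dated in the data. Some AE percentages may rise slightly.
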